4.3.2 Acute (Randomization) Phase (45 days)

If the patient meets all eligibility criteria they will be randomized at the Baseline Visit via the IWRS system. The patients will be provided with an eDiary. The study personnel will instruct the patient on the proper use of the eDiary and ensure proper understanding and use of the tool, prior to the patient leaving the office.

After randomization via the IWRS system, the patient will be dispensed a single dose of the double-blind study medication to take home for up to 45 days. This study medication is to be taken when a migraine attack reaches moderate or severe intensity on the numeric rating scale (NRS) as indicated in the eDiary. The patient will be instructed to take their study medication, as an outpatient, when (if) they have a migraine headache which reaches moderate or severe intensity **after they answer eDiary questions about their current pain and symptoms and identify their currently most bothersome, migraine associated, symptom (phonophobia, photophobia or nausea)**. The patient will complete an eDiary for up to forty-eight hours after taking study medication. The patient will telephone the study center immediately if a severe or serious adverse event occurs.

Patients will record efficacy data in their eDiary. This includes the following: onset time of headache, intensity of the headache prior to **and** at time of taking study medication. The patient should record all headache intensity leading up to dosing, but should not dose with study medication until the headache reaches moderate or severe intensity. Headache severity will be recorded using a four-point numeric rating scale (no pain, mild pain, moderate pain, severe pain) at the onset of the migraine and after dosing at time points of 15, 30, 45, 60, and 90 minutes and 2, 3, 4, 6, 8, 24 and 48 hours. The presence or absence of associated symptoms (nausea, photophobia, phonophobia) and ratings of functional disability (four-point scale: normal, mildly impaired, severely impaired, requires bedrest) will be recorded at the same time points as the headache severity ratings. Patients will also identify their currently most bothersome symptom before taking study medication. Patients will record the date and time study therapy was taken in their eDiary. Patients will also complete the migraine-specific quality-of-life questionnaire (MQoLQ) and preference of medication (PoM) 24 hours after

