6.3.2 Nausea, Phonophobia and Photophobia

The migraine associated symptoms of photophobia, phonophobia and nausea are measured on a two point scale (present or absent), using the eDiary, at the time points listed in [Table 1](#). If a subject reports the presence of a symptom, the subject is then asked to rate the severity of the symptom on a four point scale (none, mild, moderate or severe). All assessment is done using the eDiary.

The subjects are also asked to identify their most bothersome symptom on the eDiary (nausea, phonophobia or photophobia) at the onset of the migraine to be treated. The most bothersome symptom must be identified before the subject takes study medication.

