**Table 1: Estimands for the Co-Primary Objectives**

Objective	Pain Freedom at 2 hours post-dose
Population	mITT
Variable	Percent of subjects reporting no pain at 2 hours post-dose
Intercurrent Events	NC=F; RM=F;
Objective	Freedom from Most Bothersome Symptom (MBS)
Population	mITT
Variable	Percent of subjects reporting absence of their MBS at 2 hours post dose
Intercurrent Events	NC=F; RM=F; Failure to report MBS = F; Study medication taken before reporting MBS=F.

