### **5.7.2 MBS Recored After IP is Taken**

Subjects that record their MBS after taking the investigation product (IP) are considered failures for the analysis of MBS.

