#### 5.7.3.2 *Freedom from MBS at 2 Hours Post-Dose*

Freedom from each subject's MBS is assessed using the number of mITT subjects who report that their MBS (reported at migraine onset) is absent at 2 hours post-dose. The symptoms that can be nominated as the MBS (phonophobia, photophobia or nausea) are measured using a binary scale (0=absent, 1=present).

Subjects who reported their MBS before taking IP, or who did not provide an MBS are considered failures in this analysis.

Tabulations will be presented as follows:

- The number and percentage of subjects reporting each of the migraine associated symptoms (phonophobia, photophobia or nausea) as most bothersome, subjects with a missing MBS, and subjects who reported their MBS after taking study medication.
- A cross tabulation of the historical MBS (reported at screening) as rows, and the MBS reported at the onset of the treated migraine as columns. This tabulation only includes subjects with both assessments. P-value from a chi-square test will be reported along with the values and confidence limits for both Asymmetric Lambda and Symmetric Lambda.

The estimand, difference in percentage of MBS free subjects (“risk difference”) between treatment groups, is evaluated by computing the common risk difference, using CMH weights (sample size weights), stratified by the use of prophylactic migraine medication (yes or no). The risk difference will be tested at a two-sided alpha level of 0.05. Missing data at 2 hours post-dose will be imputed as failure (NC=F). Also the use of rescue medication prior to providing data at the 2 hour assessment, taking IP prior to reporting the MBS, or failure to report a MBS are events that are imputed as treatment failures. If a stratum (prophylactic medication use: yes or no) has sparse data (less than 5 subjects) then the strata will be pooled.

The results to be presented for the primary analysis of MBS include those described in items (a) through (e) for the primary analysis of pain freedom (Section 5.7.3.1). In this case, the “risk” is now the probability of being MBS free at two-hours post-dose.

The primary analysis of MBS will be repeated for the subgroups described in Section 5.2.6.

Sensitivity analyses will be conducted as follows:

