### **3.2 Freedom from MBS at 3 Hours Post Dose**

The estimand, difference in percentage of subjects with freedom from MBS at 3 hours between treatment groups was evaluated by computing the common risk difference using CMH weights (sample size weights), stratified by the use of prophylactic migraine medication (yes or no). The risk difference was tested at a two-sided alpha level of 0.05. Missing data at 3 hours post-dose was imputed as failure (NC=F). Also the use of rescue medication prior to providing data at the 3 hour assessment, taking IP prior to reporting the MBS, or failure to report a MBS are events that were imputed as treatment failures.

Results presented for this analysis included the following:

- Common risk difference with sample size, p-value, ASE, and 95% asymptotic CIs.
- Risk difference within each strata with sample size, p-value, ASE, and 95% asymptotic CIs.
- A plot of the risk differences within each strata, and common risk difference (similar to the risk difference plot produced by SAS Proc Freq).

- Common risk for each treatment with sample size, ASE, and 95% asymptotic CIs.

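### One sentence in SAP 5.7.3.2 reverses the MBS timing rule, so the definition of a co-primary endpoint fails the subjects who followed the protocol

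*SAP*

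**What the plan says.** The second paragraph of SAP 5.7.3.2 sets out who counts as a failure for the 2-hour MBS endpoint: "Subjects who reported their MBS before taking IP, or who did not provide an MBS are considered failures in this analysis".

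The same section later says, in the paragraph describing the estimand and the test, that "taking IP prior to reporting the MBS, or failure to report a MBS are events that are imputed as treatment failures". Its first tabulation bullet sets aside, as a category to be counted, "subjects who reported their MBS after taking study medication".

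Elsewhere the SAP gives the rule as follows:

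- Table 1, under intercurrent events for the MBS co-primary: "Study medication taken before reporting MBS=F".
- Section 5.7.2, which is devoted to this situation: "Subjects that record their MBS after taking the investigation product (IP) are considered failures for the analysis of MBS".
- Appendix 4, section 3.2, for MBS freedom at 3 hours: "taking IP prior to reporting the MBS, or failure to report a MBS are events that were imputed as treatment failures".

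The protocol fixes the order of events. Section 6.3.2 says "The most bothersome symptom must be identified before the subject takes study medication", and section 4.3.2 says "Patients will also identify their currently most bothersome symptom before taking study medication". Footnote 2 to the schedule of assessments makes completing the eDiary questions, including the MBS, a condition for taking the tablet.

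**The concern.** The contested sentence is an operative responder rule for a co-primary endpoint, and it points the wrong way. The protocol wants the MBS named first and the tablet taken second. The sentence classifies exactly those subjects as failures and says nothing against those who dosed first. The section that defines the endpoint therefore contains two opposite rules, and the SAP does not say which takes precedence.

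Under SAP 5.2.5 both co-primaries must be significant before the fixed sequence of 11 secondary endpoints is opened. A wrong derivation here would therefore reach well beyond the MBS result. The SAP is also the prespecified record against which an independent programmer or assessor would verify the derivation, and neither should have to infer which of two opposite statements governs.

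**Working it through.** No stated figure is in dispute, so the check is a comparison of text followed by an enumeration.

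**1. Direction of each SAP statement**

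| SAP location | Group classed as failure | Endpoint |
|---|---|---|
| 5.7.3.2, second paragraph | MBS before IP | 2-hour co-primary |
| 5.7.3.2, estimand paragraph | IP before MBS | 2-hour co-primary |
| 5.7.2 | IP before MBS | MBS analysis |
| Table 1 | IP before MBS | 2-hour co-primary |
| Appendix 4, 3.2 | IP before MBS | 3-hour supportive |

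One statement runs one way and four run the other. Three of the four govern the 2-hour co-primary; the fourth is the parallel 3-hour analysis. The tabulation bullet in 5.7.3.2 also treats late reporters as the irregular group, which fits the majority.

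**2. Consequence by reporting state**

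Each subject is in one of three states.

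| State | Contested sentence alone | The other four statements | Both applied |
|---|---|---|---|
| MBS reported, then IP taken (protocol order) | Failure | Eligible | Failure |
| IP taken, then MBS reported | Eligible | Failure | Failure |
| No MBS reported | Failure | Failure | Failure |

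Table 1, the estimand paragraph of 5.7.3.2 and Appendix 4 section 3.2 cover the third state explicitly; section 5.7.2 deals only with timing.

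Let p_B, p_A and p_N be the shares of an arm in the three states, with p_B + p_A + p_N = 1. The observed success rate in that arm is then bounded as follows:

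- intended rule: at most p_B;
- contested sentence alone: at most p_A;
- both applied: 0.

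In the last case the comparison is 0% against 0% and the test is empty. The documents give no value for p_A, so neither a subject count nor a power figure is offered. The SAP does expect the group to exist: section 5.7.2 is written for it, and section 6.1 counts subjects who took the medication before giving baseline migraine characteristics.

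**3. Reach**

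The MBS tables in SAP Appendix 1 that use the 2-hour definition are:

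- 14.2.2.2, primary: 1
- 14.2.2.2.1 to 14.2.2.2.7, subgroups: 7
- 14.2.2.3.1 to 14.2.2.3.6, sensitivity: 6

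Total: 1 + 7 + 6 = 14. Section 5.2.5 lists 11 secondary endpoints that depend on both co-primaries succeeding.

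**The case against.** The strongest reply is that this is an erratum and little more. Read in order, the SAP gives the correct rule in Table 1 and again in 5.7.2 before the reader reaches the faulty sentence, and 5.7.3.2 corrects itself a few paragraphs later. The harmful readings would announce themselves: an endpoint with no successes, or one in which only non-compliant subjects succeed, would be noticed at first output. Appendix 4 describes the 3-hour analysis in the past tense with the intended rule, which makes misprogramming of the 2-hour endpoint less likely. The protocol also contains no failure rule for MBS timing; section 9.4.1 imputes only missing 2-hour data as failure.

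Most of this stands, and it limits the practical risk. The intended rule is not in doubt, and the conflict with the protocol is that the sentence penalises the required order, not that it breaks a protocol analysis rule. The Appendix 4 wording does not show how the 2-hour endpoint was coded. Counting states or tables shows the logic and the reach of the error, not its effect on the result.

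The reply does not remove the contradiction. The text is a responder definition for a co-primary endpoint, it is complete and grammatical, and it is wrong as written. Recovering the rule requires the reader to overrule one sentence with others.

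**Conclusion.** The concern holds. One sentence in SAP 5.7.3.2 reverses the MBS timing rule, against four consistent statements elsewhere in the SAP and against the order of reporting and dosing in the protocol. Followed alone, it fails every compliant subject; followed together with the other statements, it fails every subject in both arms. It should be fixed, but the practical risk is limited because the intended rule is clear.

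This conclusion rests on the wording alone. It assumes nothing about how many subjects dosed before naming their MBS, and it does not claim that the analysis was programmed wrongly. No method, estimand, alpha, power or sample size is challenged.

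**What to change.** In the second paragraph of SAP 5.7.3.2, replace *before* with *after*, so that subjects who named their MBS after taking IP, and those who named none, are the failures. That brings the sentence into line with Table 1, section 5.7.2 and the estimand paragraph of the same section.

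Then confirm that the MBS derivation program applies this rule in the primary, subgroup and sensitivity analyses behind the 14 tables, and in the other outputs that draw on it, such as the MBS forest plots.

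The cost is one word in the SAP and one check of the derivation. No new analysis decision is needed.

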#### **5.7.4 Secondary Efficacy Endpoints Evaluated with Data from the Current Study**

If the co-primary endpoint tests are both significant, then the secondary endpoints are evaluated using a fixed sequence approach, with each test in the hierarchy conducted at  $p=0.05$ . See Section 5.2.5 for the testing order.

##### **5.7.4.1 Freedom from Photophobia, Phonophobia or Nausea at 2 Hours**

Freedom from photophobia, phonophobia, and nausea are assessed, by treatment group, by tabulating the number of mITT subjects who reported the presence of the symptom at migraine onset who then report the absence of the symptom at 2 hours post-dose. Subjects who report the symptom at baseline, but have missing data at 2 hours post-dose will be imputed as failures (NC=F). Also, subjects in the analysis set that take rescue medications on or before providing their 2 hours post-dose data are imputed as failures.

The principal measurement for the associated symptoms (phonophobia, photophobia, and nausea) is made on a binary scale (0 = absent; 1 = present). An exploratory measurement of these symptoms was also made on a 4 point Likert scale (0=none, 1=mild, 2=moderate, 3=severe).

For these three endpoints, the difference between treatment groups, is evaluated by computing the common risk difference, using CMH weights (sample size weights), stratified by the use of prophylactic migraine medication (yes or no). The risk difference is tested at a two-sided alpha level of 0.05. If a stratum (prophylactic medication use: yes or no) has sparse data (less than 5 subjects) then the strata are pooled.

The results presented for the analysis of each symptom include those described in items (a) through (e) for the primary analysis of pain freedom (Section 5.7.3.1). In this case, the “risk” is the probability of being free from the symptom of interest at 2 hours post-dose. In addition, the following display will be created for each of the 3 symptoms:

- A table showing descriptive statistics for the 4-point scale, which includes the number and percentage of subjects reporting each of the 4 symptom levels at 2 hours post-dose, and the percentage of subjects with missing data, for each treatment group. The table will include exact (Clopper-Pearson) 95% CIs for each percentage.

#### 5.7.4.2 *Pain Relief at 2 Hours*

Pain relief at 2 hours post-dose is assessed by tabulating the number of mITT subjects that report a pain level of none or mild (responses of 0 or 1 on the 4-point Likert scale) at 2 hours post-dose, by treatment group. Subjects with missing data at 2 hours post-dose will be imputed as failures (NC=F).

The results to be presented for the analysis include those described in items (a) through (e) for the primary analysis of pain freedom (Section 5.7.3.1). In this case, the “risk” is the probability of pain relief at 2 hours post-dose.

#### 5.7.4.3 *Probability of Requiring Rescue Medication within 24 Hours*

Whether or not a subject took rescue medication within 24 hours after the initial dose of study medication is tabulated, using mITT subjects, and the percentages are compared between treatment groups.

The results are presented for the analysis include those described in items (a) through (e) for the primary analysis of pain freedom (Section 5.7.3.1). In this case, the “risk” is the probability of not requiring rescue medication within 24 hours post-dose.

Rescue medications are tabulated by treatment group and overall.

Information regarding the rescue medication, including the type, date and time taken, dose, route and form of administration, and frequency, is presented in a listing by treatment group and subject.

#### 5.7.4.4 *Functional Disability Scale at 2 Hours*

Impact of treatment on subject disability is assessed using a single-question, functional disability scale. Subjects rate the level of disability they perceive as a result of their migraine in performing normal actions using a 4-point scale: Normal Function, Mild Impairment, Severe Impairment, or Required Bedrest. The proportion of mITT subjects who have a response of “normal” at 2-hours post dose will be evaluated as the endpoint of interest.

The information from the 4-point scale will be directly summarized as follows:

- A table showing descriptive statistics for the 4-point scale, which includes the number and percentage of subjects reporting each of the 4 disability levels at 2 hours post-dose, and the percentage of subjects with missing data, for each treatment group, using the observed data. The table will include exact (Clopper-Pearson) 95% CIs for each percentage.

The results to be presented for the analysis include those described in items (a) through (e) for the primary analysis of pain freedom (Section 5.7.3.1). In this case, the “risk” is now the probability of a functional disability level of “normal” at 2 hours post-dose.

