1.4 Study Rationale

Migraine is a chronic and debilitating disorder characterized by recurrent attacks lasting four to 72 hours with multiple symptoms, including typically one-sided, pulsating headaches of moderate or severe pain intensity that are associated with nausea or vomiting, and/or sensitivity to sound (phonophobia) and sensitivity to light (photophobia). The World Health Organization's (WHO) Global Burden of Disease Study ranks migraine as the third most prevalent disease worldwide [9] and the Global Burden of Disease Survey 2010 rates migraine as the seventh highest specific cause of disability worldwide. Annually, migraines affect approximately 15% of the adult population in the United States [10], comprising approximately 33 million adults. Approximately 62% of migraineurs have one or more attack per month, and approximately 25% have one or more per week [11]. Approximately 80% of individuals are unable to work or function normally during a migraine attack, with 53% reporting severe impairment and/or requiring bedrest [12, 13]. Comorbid conditions associated with migraine include depression, anxiety and cardiovascular disease [14].

While there are multiple classes of medications for the acute treatment of migraine, considerable unmet need remains, as evidenced by migraines being the seventh leading cause of disability worldwide [9]. In part, this burden is attributed to limitations of current standard-of-care pharmacotherapies, which are contraindicated for use in over 2.6 million American migraine sufferers with known cardiovascular disease as well as many others with multiple cardiovascular (CV) risk factors. The US Prescribing Information (USPI) for triptans includes warnings and precautions for migraine patients with risk factors for cardiovascular disease and states that high risk patients, including those with

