3.2 Secondary

- **Freedom from Photophobia** will be assessed by tabulating the number of subjects that report the absence of photophobia at 2 hours post-dose in the subset of subjects that reported the presence of photophobia at headache baseline.
 - **Freedom from Phonophobia** will be assessed by tabulating the number of subjects that report the absence of phonophobia at 2 hours post-dose in the subset of subjects that reported the presence of phonophobia at headache baseline.
 - **Pain Relief** (aka “headache response”), at 2 hours post-dose, will be assessed using the number of evaluable subjects that report a pain level of moderate or severe (responses of 2 or 3 on the 4 point Likert scale) at baseline and then report a pain level of none or mild (response of 0 or 1) at two hours post-dose.
 - **Freedom from Nausea** will be assessed by tabulating the number of subjects that report the absence of nausea at 2 hours post-dose in the subset of subjects that reported the presence of nausea at headache baseline.
 - The probability of **requiring rescue medication** will be assessed using the number of subjects that take rescue medication within 24 after administration of study medication (BHV3000 or placebo).
 - **Sustained pain freedom**, from 2 to 24 hours, will be assessed using the number of subjects that do not experience any headache pain through the time period of interest.
-

- **Sustained pain relief**, from 2 to 24 hours will be assessed using the number of subjects that do not use any rescue medications, and do not experience any moderate or severe headache pain through the time period of interest.
- **Sustained pain freedom**, from 2 to 48 hours, will be assessed using the number of subjects that do not experience any headache pain through the time period of interest
- **Sustained pain relief** from 2 to 48 hours, will be assessed using the number of subjects that do not use any rescue medications, and do not experience any moderate or severe headache pain through the time period of interest.
- **Pain relapse** will be assessed using the number of subjects that are pain free at 2 hours post-dose and then have a headache of any severity (response of 1, 2 or 3 on the 4 point scale) within 48 hours after administration of study medication (BHV3000 or placebo).
- The proportion of subjects able to function normally, at 2 hours, will be assessed using the number of subjects that self-report as “normal” on the **functional disability** scale.

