## **4 SUBJECT POPULATIONS**

### **4.1 Population Definitions**

The following subject populations will be evaluated and used for presentation and analysis of the data:

- Enrolled subjects: patients who sign an informed consent form and are assigned a subject identification number
- Randomized subjects: enrolled subjects who receive a randomization treatment assignment from the interactive web response system (IWRS), regardless of the treatment they actually received or subsequent withdrawal from treatment
- Treated subjects: enrolled subjects who take any amount of study therapy (rimegepant or placebo)
- Modified Intent-to-Treat (mITT) subjects: Randomized subjects who are randomized only once, take study medication, have a baseline migraine of moderate to severe intensity, and who provide at least one post-baseline efficacy data point. Subjects that re-enrolled in the study, and were randomized on two or more occasions are not included in the mITT population.

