### **1.4 Sustained Freedom from Functional Disability**

The ad-hoc sustained freedom from functional disability endpoints were:

- Sustained Freedom from Functional Disability 2 to 24 hours
- Sustained Freedom from Functional Disability 3 to 24 hours

- Sustained Freedom from Functional Disability 4 to 24 hours
- Sustained Freedom from Functional Disability 2 to 48 hours
- Sustained Freedom from Functional Disability 3 to 48 hours
- Sustained Freedom from Functional Disability 4 to 48 hours

Sustained freedom from functional disability for these time periods is defined in a manner similar to that used for sustained pain freedom from 2 to 24 hours and 2 to 48 hours.

Sustained freedom from functional disability was assessed using the number of mITT subjects who experienced normal functioning at all time points from the starting time point (2, 3 or 4 hours post-dose) through the ending time point (24 or 48 hours post-dose). Subjects with missing disability scores at 1 or fewer time points, given that they have responses of no disability at all other time points including the starting and ending time points (and 24 hours for periods through 48 hours), were considered as successes. Subjects with missing data at greater than 1 post-dose time point, missing data at either the starting or ending time point (or 24 hours for periods through 48 hours), or with any reported disability in the time period were classified as failures.

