## **2.2 Time to First Report of Absence of Various Symptoms**

For each of the following variables, two sets of Kaplan-Meier plots and tables were created:

- Time to First Report of Absence of Most Bothersome Symptom
- Time to First Report of Absence of Nausea
- Time to First Report of Absence of Photophobia
- Time to First Report of Absence of Phonophobia
- Time to First Report of Return to Normal Functioning

The first set of plots and tables was similar to those created for the time to rescue medication (using actual time). For the second set of plots, nominal (planned time point) as opposed to actual time was used for clinical event times. Censoring was measured using actual time as in all previous plots.

For both sets of analyses, the analysis population for MBS and functional disability was the set of mITT subjects. The analysis population for nausea, phonophobia, and photophobia was the subset of mITT subjects that reported the symptom as present at the onset of their study migraine. The y-axis for all plots represents the probability of the occurrence of the event of interest, and therefore are increasing from left to right.

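### The post-hoc return-to-normal-functioning analysis counts subjects who were already functioning normally at migraine onset, and no planned analysis separates them at 2 hours

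*SAP*

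**What the plan says.** Functional disability at 2 hours is the eleventh and last secondary endpoint in the fixed sequence (SAP 5.2.5). SAP Table 2 gives its population as mITT, and SAP 5.7.4.4 defines it thus: "The proportion of mITT subjects who have a response of “normal” at 2-hours post dose will be evaluated as the endpoint of interest". Protocol 3.2 words it the same way, as a state at 2 hours.

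To enter mITT on efficacy grounds a subject must "have a baseline migraine of moderate to severe intensity" (SAP 4.1). Nothing is required about function. Function is nevertheless rated at onset: protocol 4.3.2 says the functional ratings "will be recorded at the same time points as the headache severity ratings", and protocol Table 1 marks the scale at onset.

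The three associated symptoms are handled differently. SAP 5.7.4.1 counts "mITT subjects who reported the presence of the symptom at migraine onset who then report the absence of the symptom at 2 hours" post-dose.

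The unrestricted set recurs in these functional-disability analyses:
- 24 hours (SAP Table 3 and 5.7.6.1).
- 3 hours (Appendix 4, 4.3).
- Sustained endpoints (Appendix 4, 1.4): "Sustained freedom from functional disability was assessed using the number of mITT subjects who experienced normal functioning at all time points" in the period.
- Time to first return to normal functioning (Appendix 4, 2.2): "the analysis population for MBS and functional disability was the set of mITT subjects". The next sentence limits nausea, phonophobia and photophobia to subjects with the symptom at onset.

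SAP 5.7.6.5 lists functional disability twice: once with endpoints tabulated on all mITT subjects, and once with symptoms tabulated on those reporting them at baseline.

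**The concern.** A return to normal presupposes impairment. In the Appendix 4 analysis a subject who rated function as normal at onset has an event at the first post-dose normal rating, which can be the 15-minute entry. The early part of the curve and the median then partly describe how many subjects were never impaired, in both arms.

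The 2-hour endpoint raises a milder question. It asks who is normal at 2 hours, which a never-impaired subject can legitimately be. If such subjects fare alike in both arms, however, they add the same amount to each response rate and shrink the difference. The 2-hour table in SAP 5.7.4.4 does not break the result down by onset level, and the every-timepoint tables are post-dose. A reader could not tell how many normal ratings at 2 hours represent recovery.

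**Working it through.** **Inputs.** About 550 treated subjects per arm (protocol 9.2, SAP 5.1), 1:1 allocation, two-sided 0.05. The share f normal at onset is in neither document. The only clue is protocol 1.4: "Approximately 80% of individuals are unable to work or function normally during a migraine attack", which leaves about 20%. That is background on attacks in general, and treated attacks here must be moderate or severe, so f may well be lower. I use 5%, 10% and 20%.

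**The plan's own figure.** No power or response rate is stated for functional disability. The stated power of more than 95% for pain freedom does reproduce: 31.4% vs 15.3% at 550 per arm gives more than 99.9%.

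**Return-to-normal median.** Suppose onset-normal subjects have their event at the first entries and nobody is censored earlier. If a share r of impaired subjects has recovered, the curve stands at f + (1 − f)r. Setting this to 0.5 gives r = (0.5 − f)/(1 − f).
- f = 5%: 0.45/0.95 = 47%.
- f = 10%: 0.40/0.90 = 44%.
- f = 20%: 0.30/0.80 = 37.5%.

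The reported median is therefore earlier than the median among subjects with something to recover.

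**2-hour difference.** Let impaired subjects reach normal at rates q1 and q0, and let onset-normal subjects remain normal at rate s in both arms. Each all-mITT rate is fs + (1 − f)q, so the difference is (1 − f)(q1 − q0).

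Illustration with assumed values q1 = 35%, q0 = 25%, s = 80%, using a two-proportion z test with pooled null variance:

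| f | All mITT, 550 per arm | Power | Impaired at onset | Power |
|---|---|---|---|---|
| 5% | 37.25% vs 27.75%, difference 9.5 points | 92.1% | 522 per arm, 10 points | 94.2% |
| 10% | 39.5% vs 30.5%, difference 9 points | 88.0% | 495 per arm, 10 points | 93.1% |
| 20% | 44% vs 36%, difference 8 points | 77.4% | 440 per arm, 10 points | 90.0% |

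Over q0 of 20–30%, a difference of 8–12 points and s of 80–100%, restriction gains about 1–5 power points at f = 5%, 2–11 at 10% and 7–21 at 20%.

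**When dilution disappears.** Keep f = 20% but let the drug preserve function, with onset-normal subjects staying normal in 85% vs 75% (assumed). The all-mITT rates are 0.2 × 0.85 + 0.8 × 0.35 = 45% and 0.2 × 0.75 + 0.8 × 0.25 = 35%. The difference is 10 points. The standard error is 0.0295 under the null and 0.0294 under the alternative, so power is Φ((0.10 − 1.96 × 0.0295)/0.0294), about 92%. That is above the 90.0% of the restricted test.

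**Type I error.** Simulation of the all-mITT test gave 5.1% at f = 0 and 5.2% at f = 20%.

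**The case against.** The strongest reply concerns the 2-hour test. A reader might infer that this alpha-controlled test is itself diluted and that its population should be replaced. The documents do not support that.
- The endpoint is a state. It matches its objective in protocol 2.2 and SAP 1.2.2 and its definition in protocol 3.2. Restricting it would change the estimand and, if made in the SAP alone, would put the SAP in conflict with the protocol.
- Onset-normal subjects are not automatic successes. Worsening, a missing 2-hour rating or rescue at or before 2 hours makes them failures.
- Keeping function as an attack develops is a benefit too. If the drug provides it, the dilution vanishes, as shown above.
- The 20% is not a trial input. In the 5–10% range the assumed power loss is about 2 to 5 points.

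All of this stands. So does the limit on consequences: type I error is unaffected, and as the last item in the sequence this test cannot affect another.

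None of it rescues the return-to-normal analysis, whose population does not fit its title. That analysis is post hoc and outside the controlled sequence, which limits the damage but leaves the curve misleading. SAP 5.7.6.5 may already intend a baseline-restricted tabulation, but its wording points both ways.

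**Conclusion.** The population of the return-to-normal Kaplan-Meier analysis is wrong as written. Its median corresponds to 47%, 44% or 37.5% recovery among impaired subjects at f = 5%, 10% or 20%, assuming onset-normal subjects score at once and without earlier censoring. The actual size depends on f, which the onset ratings will show.

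For the 2-hour endpoint the specified all-mITT test is sound. Its difference may be reduced by up to the factor (1 − f), a fifth at f = 20%, only if onset-normal subjects respond equally in both arms. The power figures rest on assumed response rates. The gap is that nothing planned clearly separates recovery from function that was never lost; supportive analyses would be a cheap improvement.

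**What to change.** 1. In Appendix 4 section 2.2, restrict the return-to-normal analysis, with actual and nominal times, to mITT subjects rated below normal at onset, as that section does for the three symptoms. Apply the same restriction to its pooled version in section 2.3.
2. Keep the 2-hour endpoint on all mITT subjects. Add a supportive analysis of subjects impaired at onset and a cross-tabulation of onset by 2-hour rating, by arm.
3. Add the same supportive analysis for the 3-hour, 24-hour and sustained functional-disability endpoints.
4. In SAP 5.7.6.5, state which denominator applies to functional disability.

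The cost is a somewhat smaller denominator in the restricted analyses and a few extra tables from ratings already collected. No controlled test changes. This matters because Appendix 4 is post hoc and written largely in the past tense, so one cannot assume the data are still blinded.
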